As we tested multiple outcome measures for association with DG status (Aim 1) and for association with diet among DG cases (Aim 2), for each of the outcomes considered, we identified the relevant covariates to adjust for. Using the steps described below, we determined the subset of covariates to be included in subsequent models for each outcome.

- 1. Using the information provided in step #8 above, we identified all variables that were to be initially considered as potential confounders for each outcome measure.
- 2. With these variables as predictors and the outcome measure of interest as the response variable, we used the R package *glmnet* to fit a generalized linear model with lasso regularization.
 - a. We used 10-fold cross-validation to determine the optimal lambda value.
 - b. We identified the subset of variables with non-zero coefficients and flagged these as covariates for subsequent models of the outcome.
 - c. Please note: This approach assumed observations were independent and did not take into account the shared familial structure of the dataset. As described below, in later analyses we used a mixed-model approach to account for relatedness among family members in the study.

Dividing our full cohort into independent discovery and validation sets:

Although data on 73 outcome variables were collected, our study was only adequately powered to test ~20 hypotheses due to the need to correct for multiple testing. As we sought both to test phenotypic differences between DG cases and controls, and also to test phenotypic differences associated with diet among cases, this substantially reduced the number of phenotypes we could consider without compromising the power of the data set. In order to find a balance between our desire to maintain adequate statistical power and our obligation to find differences in the data wherever they might exist, we first divided our sample into independent "discovery" and "validation" sets. We used the discovery set to identify the 10 outcome measures of greatest interest (smallest p value). We then used this subset of outcomes for a focused analysis of the validation set at an appropriate Bonferroniadjusted significance threshold.

- 1. We randomly selected ~25% of Part 2 study subjects for assignment to the discovery set.
 - To ensure independence of the discovery and validation sets, siblings were always assigned to the same set.
- 2. We assigned the remaining 75% of study subjects to the validation set.

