- We repeated the random assignment process until an appropriate mix of DG cases/controls and dairy-exposed/non-exposed cases (close to original distribution in the full dataset) was achieved in each set.

Using the discovery data set to rank order outcome variables to test in the validation data set:

- In the discovery set, we fitted a mixed-effect regression model (linear, logistic, or ordinal) for each outcome variable that included DG status and all necessary covariates as predictors.
- 2. The mixed model approach allowed for clustering at the family level and therefore took into account relatedness among study subjects.
- 3. We ranked the models by resulting p-value for the DG status regression coefficient, and selected the 10 top-scoring outcomes between cases and controls.
- Even if no models showed significance at raw p<0.05 for association with DG, we choose the 10 outcomes with the smallest p-values.

Aim 1: Identify phenotypes associated with DG

1. We fit comparable models for the 10 outcomes showing the smallest p values in the

discovery set using data from the independent validation set.

2. Our goal was to identify any outcomes whose models showed significant association with DG status at the Bonferroni-adjusted p-value threshold ($\alpha = 0.05/20 = 0.0025$) in the validation set. There were none.

Aim 2: Identify phenotypes associated with diet among DG cases

While the random assignment process described above yielded a discovery set with a satisfactory number of both cases and controls to assume it was representative of the full study population, the number of dairy-exposed cases and non-exposed cases in the discovery set was not large enough to confidently consider it a representative sample. For this reason, we tested the same 10 outcome variables as above for association with diet among DG cases.

- 1. We filtered the discovery set generated as described above to include only DG cases.
- Using the discovery set, we fitted a mixed-effect regression model (linear, logistic, or ordinal) for each of the 10 selected outcome variables that included milk exposure and all necessary covariates as predictors.
- 3. Our goal was to identify any outcomes whose models showed significant association with diet among cases at a Bonferroni-adjusted p-value threshold ($\alpha = 0.05/20 = 0.0025$) in the discovery set. There were none.

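### The SAP contradicts itself on which cases carried the diet tests, and the diet null covers only the 10 outcomes that were tested

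*SAP*

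**What the plan says.** **Which cases.** The SAP's opening summary splits 350 children (206 cases, 144 controls) into a discovery set of 87 and a validation set of 263. It then says that the 10 outcomes with the smallest discovery p-values were tested in the validation set for two things: DG status and, among cases, milk exposure in the first year. The section on dividing the cohort agrees: "We then used this subset of outcomes for a focused analysis of the validation set".

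The Aim 2 section says otherwise. Step 1: "We filtered the discovery set generated as described above to include only DG cases". Step 2: "Using the discovery set, we fitted a mixed-effect regression model (linear, logistic, or ordinal) for each of the 10 selected outcome variables". Step 3 applies the threshold 0.05/20 = 0.0025 in the discovery set and reports that no outcome met it. The paragraph above these steps says that "the number of dairy-exposed cases and non-exposed cases in the discovery set was not large enough to confidently consider it a representative sample".

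**Which outcomes.** The ranking section, step 3, reads: "We ranked the models by resulting p-value for the DG status regression coefficient, and selected the 10 top-scoring outcomes between cases and controls". Aim 2 uses those outcomes: "we tested the same 10 outcome variables as above for association with diet among DG cases". The reason given for a short list is that "our study was only adequately powered to test ~20 hypotheses due to the need to correct for multiple testing".

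**What the question was.** The Protocol's Background and Goals makes the diet question follow on cases differing from controls. Specific Aim 2 carries no such condition.

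**The concern.** The two accounts of the data set cannot both be right, and the difference decides how much the diet null is worth. A null in three quarters of the cases is moderately informative. A null in one quarter of them, in a set that the SAP itself considers too thin in exposed and unexposed children, says little. Specific Aim 2 is one of only two aims, and a reader cannot tell which null is being reported.

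The second matter is scope. It concerns what the null covers, not how precise it is. No diet test is described outside the 10 outcomes. The cleaning section's step 12 gives only descriptive summaries by dairy exposure for the rest. A conclusion that diet is not associated with developmental outcomes in DG would go further than the tests did.

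**Working it through.** **1. The plan's own figures.** 206 + 144 = 350 and 87 + 263 = 350. The threshold 0.05/20 = 0.0025 reproduces: ten DG-status tests plus ten diet tests. The diet share of the error is 10 × 0.0025 = 0.025. The SAP gives no inputs for its limit of about 20 hypotheses, so that cannot be reproduced.

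**2. Cases in each set (assumed proportional).** The SAP does not give the counts, but it repeated the random split until a suitable mix of cases and controls and of "dairy-exposed/non-exposed cases (close to original distribution in the full dataset) was achieved in each set".
- Discovery: 206 × 87/350 = 51.2 cases, with 144 × 87/350 = 35.8 controls.
- Validation: 206 × 263/350 = 154.8 cases.

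**3. What each set could detect.** Assumptions: two exposure groups, exposed share f, a continuous outcome with SD 1, no covariates and no family clustering. The two-sided critical value at 0.0025 is 3.023, and 80% power adds 0.842.
- SE = sqrt(1/(nf) + 1/(n(1−f))). This is 2/√n at f = 0.5 and 2.5/√n at f = 0.8 (or 0.2).
- Detectable effect = (3.023 + 0.842) × SE.
- Power at 0.5 SD = Φ(0.5/SE − 3.023).

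| Exposed share | Quantity | Discovery, 51.2 | Validation, 154.8 |
|---|---|---|---|
| 50% | Detectable effect | 3.865 × 2/7.156 = 1.08 SD | 3.865 × 2/12.442 = 0.62 SD |
| 50% | Power at 0.5 SD | Φ(1.789 − 3.023) = 11% | Φ(3.110 − 3.023) = 53% |
| 80% (or 20%) | Detectable effect | 1.35 SD | 0.78 SD |
| 80% (or 20%) | Power at 0.5 SD | Φ(1.431 − 3.023) = 6% | Φ(2.488 − 3.023) = 30% |

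**4. Coverage.** 73 − 10 = 63 outcomes had no formal diet test. This is an upper figure: step 8c of the cleaning section flagged outcomes by aim, and the number flagged for Aim 2 is not given.

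**5. Does ranking on case-control status cost power for diet?** Take one outcome with a 0.5 SD milk effect among 72 independent null outcomes. Its case-control contrast is f × 0.5 plus any difference s between unexposed cases and controls. The SE of that contrast in the discovery set is sqrt(1/51.2 + 1/35.8) = 0.218. The outcome is selected if at most 9 of the 72 have a smaller p-value.

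| Difference s (SD) | Selected, f = 30% | Selected, f = 50% |
|---|---|---|
| 0 | about 22% | 37% |
| +0.25 (same direction as the milk effect) | 63% | 78% |
| −0.25 (opposite direction) | 18% | 14% |

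Selection by chance alone is 10/73 = 14%. The chance of being selected and then significant in 155 cases at f = 50% is 0.37 × 0.535 = 20% with s = 0, and 0.78 × 0.535 = 42% with s = +0.25. Testing all 73 outcomes for diet in the same cases at 0.025/73 gives 32%. The ranking therefore loses in one case and gains in the other. The documents give neither f nor s.

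**6. Error from a second look.** These figures treat the outcomes as independent and apply if a result from either look may be claimed.
- Refit in all 206 cases after a validation-set look: the two statistics correlate at sqrt(154.8/206) = 0.867, which gives 0.00405 per outcome. Over ten: 1 − (1 − 0.00405)^10 = 0.040.
- Refit in all 206 after a discovery-set look: correlation sqrt(51.2/206) = 0.499, 0.00485 per outcome, 0.047 over ten.
- Adding the ten Aim 1 tests (1 − 0.9975^10 = 0.0247) gives 0.064 and 0.071, against 0.05.
- Refit in the validation set after a discovery-set look: the sets are independent, so 1 − 0.9975^20 = 0.049 over the ten diet outcomes, against 0.025.

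**The case against.** The strongest reply on the data set is that the word discovery in the Aim 2 steps is a drafting slip. Two other places in the SAP point to the validation set, and the Aim 2 paragraph's own remark on small numbers would make the discovery set an odd choice. That may be so. But the word appears in the filter, the model fit and the reported result, and nothing in the documents settles it.

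On scope, the reply is stronger. The SAP says openly that it reuses the 10 outcomes and gives a power reason. Its null is worded for those models only, so the SAP itself does not overclaim. The conditional wording in the Protocol's goals also supports looking at diet where cases and controls differ. This largely stands: the choice is legitimate and disclosed. What remains is that Specific Aim 2 is unconditional, so the limit has to travel with the conclusion.

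A reader might go further and infer that ranking on a case-control p-value was the wrong screen and cost the diet aim power. The documents do not support that. If unexposed cases equal controls and 30% to 50% of cases are exposed, there is a loss in the validation set. If unexposed cases differ from controls by 0.25 SD in the same direction as the milk effect, the loss in that set disappears or reverses. A difference in the opposite direction makes it worse.

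**Conclusion.** The contradiction over the data set is certain from the text. Under a proportional split, a two-group exposure with half exposed, a continuous outcome and no clustering, it is the difference between a null from about 51 cases (detectable effect 1.08 SD, 11% power at 0.5 SD) and one from about 155 (0.62 SD, 53%). At 80% exposed the detectable effects are 1.35 and 0.78 SD. The model may not use a two-group exposure: the SAP speaks of exposed and non-exposed cases but names the predictor only as milk exposure.

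The scope point is a limit on inference, not an error. The null covers 10 outcomes and leaves up to 63 without a formal diet test. The direction of any power effect from the ranking is unknown. Both matters should be put right before Aim 2 is interpreted.

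**What to change.** 1. Reconcile the opening summary, the section on dividing the cohort and Aim 2 steps 1 to 3. State which cases carried the diet tests and how many were exposed and unexposed. If it was the discovery set, run the same 10 diet models in the validation-set cases at 0.0025, as the summary describes. Report both results, labelled as done after the first were known.
2. Confine the Aim 2 conclusion to the 10 outcomes, and list the outcomes flagged for Aim 2 that had no formal diet test.

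Optional and exploratory only: diet estimates with intervals in all 206 cases, for the 10 or for every outcome flagged for Aim 2, labelled post hoc and without familywise control. The 20 planned tests already spend the 0.05, so a 206-case refit at 0.0025 cannot support a confirmatory claim.

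**Cost.** Wording, and at most ten refits on existing data for the required steps. The optional analysis would add up to 73 fits. Aim 1 is unchanged. The real price of any refit is that it is a second look, with the error shown in step 6 of the working, and it must be reported as one.

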Statistical Analysis Plan

for

Study Protocol

Intervention and Outcomes in Duarte Galactosemia

Principal Investigator [name]

IRB00081271

NCT02519504

Date 04/01/2019

Statistical Analysis Plan:

Our Statistical Analysis Plan, prepared in follow-up to multiple meetings of a "Data Analysis Subgroup" from our research team, is described below. In short, data were cleaned and relevant covariates were identified for each outcome. Next, our cohort of 350 volunteers (206 cases and 144 controls) was randomly subdivided into independent "discovery" (n=87) and "validation" (n=263) sets that were approximately balanced with regard to case/control composition and covariates. We then tested each of the 73 outcome variables collected for each subject for possible association with case/control status using data from the discovery cohort; though none met the bar for statistical significance after multiple test correction we simply ranked them by ascending p value. Finally, we tested the 10 outcomes with the smallest p values from this ranking for (a) possible association with case/control status in the validation set, and also (b) possible association among cases in the validation set with milk exposure in the first year of life. All statistical analyses were performed in R.

How the data were cleaned:

- 1. We imported study data from REDCap (PCORIDGStudy_R_2017-XX-XX_XXX.r) into R.
- We filtered subjects by participation status to include only those who completed both Part 1 and Part 2.
- 3. We filtered out subjects marked for exclusion from analysis (e.g. after testing we realized they should have been excluded).
- 4. We filtered out subjects whose DG status was unknown.
- 5. We created a new variable representing the highest education level of either parent/guardian.
- 6. We created a new ordinal variable for breast milk exposure.
 - Value (0, 1, 2, or 3) indicating the number of time intervals (birth to 1 month, 2 to 6 months, 7 to 12 months) during which the subject drank at least some breast milk.
- We created new variables for average ABERS latency values at each wave (i.e., average "aber_w1_lat" and "aber_st_w1_lat").
- 8. For each variable in the dataset we:

- a. Indicated category label: administrative variable, covariate, DG status variable, dairy exposure variable, or outcome variable.
- b. For covariates, we indicated whether the variable should be considered in Aim 1 (DG/non-DG analysis), Aim 2 (DG-only diet analysis), or both.

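### The SAP contradicts itself on whether the Aim 2 (diet) result came from cases in the discovery set or in the validation set

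*SAP*

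**What the plan says.** The cohort of 350 (206 cases, 144 controls) was split into a discovery set of 87 and a validation set of 263. Siblings were kept together so that the sets would be independent. The discovery set was used to rank 73 outcomes by their association with case status, and the ten with the smallest p-values were carried forward.

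For the diet question the SAP gives two accounts.

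- **Validation set.** The opening summary says these ten outcomes were examined for "possible association among cases in the validation set with milk exposure in the first year of life". The section on dividing the cohort supports this by context. It names the diet comparison as one of its two purposes ("also to test phenotypic differences associated with diet among cases") and then says: "We then used this subset of outcomes for a focused analysis of the validation set".
- **Discovery set.** Aim 2, step 1: "We filtered the discovery set generated as described above to include only DG cases". Step 2: "Using the discovery set, we fitted a mixed-effect regression model". Step 3 applies the 0.0025 threshold and reports the outcome: "in the discovery set. There were none".

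The paragraph that introduces those three steps says that "the number of dairy-exposed cases and non-exposed cases in the discovery set was not large enough to confidently consider it a representative sample". It gives this as the reason for reusing the Aim 1 outcomes.

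**The concern.** Diet is one of the two Specific Aims in the protocol, and the finding that no outcome met the threshold is the whole of its stated result. The two sets share no participants, so the two accounts cannot describe the same test. A reader cannot tell from the text whether that result rests on roughly three quarters of the cases or roughly one quarter.

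If the ten diet models were run on the discovery set alone, the result could miss all but very large differences. It would also come from a set that the SAP itself doubts for this purpose. If they were run on the validation set, the text of three consecutive steps is wrong, and the sentence reporting the result names the wrong data.

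**Working it through.** **1. The plan's own figures.** 206 + 144 = 350 and 87 + 263 = 350, so the counts agree. The threshold 0.05/20 = 0.0025 reproduces exactly. The 20 matches ten case/control tests plus ten diet tests.

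**2. The statements side by side.**

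| Place in the SAP | Set for the diet test | Diet result given? |
|---|---|---|
| Opening summary, item (b) | Validation, explicit | No |
| Dividing our full cohort | Validation, by context | No |
| Aim 2, step 1 (filter) | Discovery, explicit | No |
| Aim 2, step 2 (model) | Discovery, explicit | No |
| Aim 2, step 3 (judge) | Discovery, explicit | Yes: none met 0.0025 |

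The opening summary is offered as a short form of the plan that follows, so the two accounts are most naturally read as describing one analysis. The Aim 2 section describes no diet test in the validation set. The SAP says the random split was repeated until the exposure mix in each set was close to that of the full data, but it gives no exposed and non-exposed counts by set.

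**3. Cases in each set.** The SAP describes the split only as approximately balanced, so a proportional split is an assumption:

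- discovery: 206 × 87/350 = 51.2, about 51
- validation: 206 × 263/350 = 154.8, about 155
- ratio: 51/155 = 0.33

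**4. What the difference could mean (illustration).** Assumptions not in the documents: two-sided test, binary exposure with 20% to 50% of cases in the smaller group, continuous outcome with SD 1, no clustering or covariates, normal approximation.

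- se = √(1/n₁ + 1/n₂)
- power = Φ(d/se − 3.023), where 3.023 is the critical value for two-sided 0.0025
- minimum detectable difference at 80% power = (3.023 + 0.842) × se

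| Cases | Exposure split | se | Power, 0.8 SD | Power, 0.5 SD | Detectable at 80% |
|---|---|---|---|---|---|
| 51 | 25.5 / 25.5 | 0.280 | 43% | 11% | 1.08 SD |
| 51 | 10.2 / 40.8 | 0.350 | 23% | 6% | 1.35 SD |
| 155 | 77.5 / 77.5 | 0.161 | 98% | 54% | 0.62 SD |
| 155 | 31 / 124 | 0.201 | 83% | 30% | 0.78 SD |

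Using the noncentral t instead, power for 0.8 SD is 20–38% with 51 cases and 82–97% with 155. The detectable difference is larger by a factor of √(155/51) = 1.74 in the discovery set, whatever the exposure share, provided the share is the same in both sets.

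**The case against.** The strongest reply is that steps 1–3 contain a copying slip. It would be odd to call the discovery set too thin in exposed and non-exposed cases and then run the final diet tests in it. The remark makes better sense as an explanation of why no separate diet ranking was attempted there. The summary and the cohort-division section also point to the validation set. This reading is plausible, and it may well be right.

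It does not close the matter, and a reader might draw either of two firmer conclusions from it.

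- *That a slip leaves the diet result intact.* The documents do not show this. The summary says where diet was tested but gives no diet result. The only stated null is attached to the discovery set. If the set name is wrong, the output must still confirm that the null is the validation-set null.
- *That the validation-set diet test was never done.* This does not follow either. The summary says in the past tense that it was. The supportable statement is that the Aim 2 section describes no such test.

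The statement that "our study was only adequately powered to test ~20 hypotheses due to the need to correct for multiple testing" might also be offered as evidence for the validation set. It does not separate the readings, because ten plus ten tests make 20 whichever set the diet models used.

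A further fair point is that the power figures rest on assumed effects. At 0.8 SD the validation set looks adequate, but at 0.5 SD it is also weak. The choice of set is therefore not simply adequate against inadequate.

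**Conclusion.** The contradiction is real and stands in the current SAP text. It must be resolved because it concerns the sole stated result for one of the study's two aims. The documents do not establish which set was analysed, and this point does not claim that the wrong one was.

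The sturdiest measure of size is the case ratio of about 0.33, which rests only on a roughly proportional split. The power and detectable-difference figures are secondary. They depend on the assumed exposure share and effect size, and they do not cover the logistic, ordinal or family-clustered models that the SAP also allows. The contradiction itself depends on none of these assumptions.

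**What to change.** 1. Check the analysis code and output to establish which set was used for the Aim 2 tests.
2. Reconcile the opening summary with Aim 2, steps 1–3. Name the set and give its numbers of exposed and non-exposed cases.
3. If the output shows the validation set was used, correct steps 1–3 and confirm from that output that no outcome met 0.0025.
4. If the discovery set was used and no validation-set diet output exists, run the ten diet models among validation-set cases, as the opening summary specifies, and base the Aim 2 conclusion on them.

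The cost is a code check, a text correction and at most ten models on data already held. No new data are needed.

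### Aim 2 is assigned to two different data sets, and on either reading it leaves out diet data from part of the 206 cases for little or no protection against error

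*SAP*

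**What the plan says.** The SAP's opening summary reports that "our cohort of 350 volunteers (206 cases and 144 controls) was randomly subdivided into independent" discovery (87) and validation (263) sets. Outcomes were chosen in the discovery set on the case-control comparison: "We ranked the models by resulting p-value for the DG status regression coefficient, and selected the 10 top-scoring outcomes between cases and controls". Milk exposure played no part in that choice.

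The SAP then describes the diet analysis in two ways.

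- **Opening summary, item (b):** the 10 outcomes were tested for "possible association among cases in the validation set with milk exposure in the first year of life".
- **Aim 2 section, step 1:** "We filtered the discovery set generated as described above to include only DG cases". Step 2 fits the models in the discovery set, and step 3 looks for "significant association with diet among cases at a Bonferroni-adjusted p-value threshold ($\alpha = 0.05/20 = 0.0025$) in the discovery set". It reports that none was found.

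The Aim 2 section also explains why diet did not get its own ranking of outcomes: "the number of dairy-exposed cases and non-exposed cases in the discovery set was not large enough to confidently consider it a representative sample". The documents give no counts of exposed and non-exposed cases, no power for Aim 2, and no reason for leaving the remaining cases out of the diet tests.

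**The concern.** Two things look wrong. First, the summary and the Aim 2 section cannot both be right about the data behind the diet null. The Aim 2 section also tests in a set that it has just called too small in exposed and non-exposed cases to be representative.

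Second, neither version uses every case. Holding data out guards against choosing and testing on the same signal. Here the choice was made on cases against controls and the test is exposed against non-exposed cases, so the usual reason for holding data out largely falls away for Aim 2.

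Diet is one of the two Specific Aims in the protocol, whose background describes providers divided over soy formula and milk. A null from a fraction of the measured cases is weaker evidence than the study could give.

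**Working it through.** **Inputs from the SAP.** 350 = 206 cases + 144 controls = 87 discovery + 263 validation. The threshold reproduces: 10 outcomes × 2 aims = 20 tests, and 0.05/20 = 0.0025.

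**Assumptions not in the documents.** Two-sided tests; cases divided in proportion to set size; exposed share 50%, 30% or 20%; true difference 0.4 or 0.5 SD.

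**1. Cases per set.** 206 × 87/350 = 51.2 and 206 × 263/350 = 154.8, so about 51 or 155. About 75% of cases go unused if the Aim 2 section is right, and about 25% if the summary is right.

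**2. Does choosing on DG status bias the diet test?** Take n cases in one set, n1 exposed and n0 not, with outcome variances s1² and s0². The selecting contrast involves the case mean; the diet contrast is the exposed mean minus the non-exposed mean. Their covariance is

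(n1/n)(s1²/n1) − (n0/n)(s0²/n0) = (s1² − s0²)/n,

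which is zero when the variances are equal. Calculated for regression models with covariates and a family random effect:

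- Selection and diet test both in the discovery set, equal variances, same covariates: correlation 0.
- Selection in discovery, diet test in validation: 0.
- Selection in discovery, diet test in all cases: mean about 0, largest 0.10 over 200 draws.
- A selection covariate omitted from the diet model: mean about 0, largest 0.09.
- SD 1.5 times larger in exposed cases: mean 0.25 for the discovery diet test and 0.12 for the all-case test.

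**3. Error rate under no diet effect.** Simulation with 73 correlated outcomes and sibling correlation, choosing the top 10 on DG status in discovery. The figure is the chance of any of the 10 diet tests crossing 0.0025; the nominal bound is 10 × 0.0025 = 0.025, and the simulation error is about 0.003.

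| Setting | Discovery | Validation | All cases |
|---|---|---|---|
| Equal SD, 50:50 | 0.023 | 0.025 | 0.026 |
| Equal SD, 30:70 | 0.025 | 0.023 | 0.022 |
| SD ratio 1.2, 30:70 | 0.027 | 0.027 | 0.028 |
| SD ratio 1.5, 30:70 | 0.047 | 0.027 | 0.031 |
| SD ratio 1.5, 50:50 | 0.046 | 0.029 | 0.032 |

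At a nominal 0.05 per test and SD ratio 1.5, the all-case rate was 0.055 (30:70) and 0.059 (50:50), against 0.051 and 0.050 in validation. A true DG effect of 0.4 SD left the all-case rate over the 10 tests at 0.026.

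**4. Power.** With exposed share p and difference d in SD units, power ≈ Φ(d√(n p(1−p)) − 3.023), where 3.023 is the critical value for two-sided 0.0025. For d = 0.5 and p = 0.5:

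- n = 51: 1.785 − 3.023 = −1.238, power 10.8%
- n = 155: 3.112 − 3.023 = 0.089, power 53.6%
- n = 206: 3.588 − 3.023 = 0.565, power 71.4%

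| Assumption | 51 cases | 155 cases | 206 cases |
|---|---|---|---|
| 0.5 SD, 50:50 | 10.8% | 53.6% | 71.4% |
| 0.5 SD, 30:70 | 8.3% | 43.2% | 60.5% |
| 0.5 SD, 20:80 | 5.5% | 29.7% | 43.9% |
| 0.4 SD, 50:50 | 5.5% | 29.7% | 43.9% |
| SD detectable at 80% power, 50:50 | 1.08 | 0.62 | 0.54 |

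The formula ignores covariate adjustment and sibling cases.

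**5. Cost of a second look.** The all-case statistic correlates with the subset statistic by √(155/206) = 0.87 or √(51/206) = 0.50. By normal approximation, the chance under the null that either look crosses 0.0025 is 0.0041 or 0.0049 per test.

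**The case against.** The strongest reply is that the split was a deliberate compromise. The SAP section on dividing the cohort explains that 73 outcomes were too many for the available power. One validation set and one family of 20 tests across both aims is a valid design. That section also speaks of a focused analysis of the validation set, which agrees with the summary, so the discovery wording under Aim 2 may be a drafting slip. If so, the loss is about a quarter of the cases. This stands, and it makes the point one of efficiency on that reading. It does not remove the contradiction. The need to choose outcomes also does not require dropping cases from the diet test.

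A reader might go further and infer that the two contrasts are simply independent, that the split does nothing for Aim 2, and that the all-case analysis could replace the reported one at no cost. The documents do not support that. The SAP lets covariates differ between aims and uses logistic and ordinal mixed models as well as linear ones; zero correlation is exact only in linear models with equal variances and matching covariates. With clearly unequal variances the validation set does give modest protection. The Aim 2 section, read literally, involves no held-out data at all. And because the SAP already reports the null, an all-case analysis is a second look.

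**Conclusion.** The point holds as a contradiction to reconcile and an avoidable loss of power. On the summary's reading, the diet test has 54% power where 71% was available; on the Aim 2 section's reading, 11%. Both comparisons assume 0.5 SD, an even exposure split and proportional division of cases. Under uneven exposure all the figures fall but their order stays the same. Using all cases costs little in error control: none detectable with equal variances, and about 0.031 to 0.032 over the 10 tests, against 0.025, at an SD ratio of 1.5.

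A reader might also infer that the published null rests on about 51 cases, or that a real diet effect was missed. Neither follows. The documents do not settle which set was used, and they give no effect sizes or exposure counts. The criticism is confined to Aim 2: for Aim 1 the same contrast selects and tests, so the split is needed there.

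**What to change.** 1. Reconcile the opening summary with Aim 2 steps 1 to 3, and state which set produced the reported null and how many exposed and non-exposed cases it contained.
2. Add the milk-exposure model for the same 10 outcomes in all 206 DG cases at 0.0025, with exposed and non-exposed counts, confidence intervals and a variance-robust sensitivity analysis.
3. Label this analysis post hoc, because the subset result is already known, and report it beside that result, not in place of it. State that the outcomes were chosen on DG status.
4. Leave Aim 1 unchanged.

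The cost is SAP wording and ten model re-runs with their sensitivity versions; no new data are needed. The statistical price is a chance of about 0.004 to 0.005 per test that either look crosses the threshold under the null, and slight inflation if variances clearly differ.
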